### 1.3 Version history of the CRF

| Version Number | Date       | Description       |
|----------------|------------|-------------------|
| 1.0            | 06/04/2018 | First version     |
| 1.1            | 08/06/2018 | Update BCVA score |

### 2. INTRODUCTION

### 3. STUDY OBJECTIVES

### 3.1 Primary Objectives

To explore the efficacy of NORFLO® ORO in RAU, measured as a long-term reduction of the frequency and severity of relapses, in patients with HLA-B27-associated uveitis, under conditions of routine medical practice. The

Statistical Analysis Plan Version no. 1.0 – 20/07/2020

Protocol Code NORFLO-ORO-16 EudraCT number NA

reduction of the mean number of relapses per patient between the year before study treatment and the study period will be also assessed.

### 3.2 Secondary Objectives

The secondary objectives of this study included:

- the evaluation of the improvement of side effects due to HLA=B27-associated uveitis such as IOP, cystoid macular edema, keratopathy and synechia;
- the evaluation of the improvement in uveitis-related symptoms (BCVA and symptoms measured by VAS like ocular pain, photophobia, floaters and blurred vision);
- the evaluation of cell damage and inflammation reduction in patients with HLA-B27-associated uveitis;
- the evaluation of the patients' attitude towards the study treatment;
- the evaluation of the safety profile of the study product.

### 4. STUDY METHODS

## 4.1 Study Design

This was a multicenter, double blind, placebo-controlled and randomized study. This study was conducted in compliance with both European and FDA requirements.

Patients eligible for participation in this study, as part of their routine medical care, received NORFLO® ORO or placebo in addition of the conventional therapy. In the study, patients were followed up to 1 year. This study included patients with HLA-B27-associated relapsing uveitis. Participating sites were encouraged to enroll patients in both cohorts (NORFLO® ORO or placebo), through an e-based randomization system in order to minimize bias in patients' selection.

### **4.2** Treatment Administration

Sixty subjects with HLA-B27-associated uveitis were enrolled and they were divided into 2 groups, 30 received the treatment and 30 the placebo, in addition to conventional therapy. In Italy 46 patients were recruited.

Each subject received a single dose of either placebo or NORFLO® ORO two times a day for 1 year. Subjects were assigned to the treatments in a random order. Evaluations were taken at baseline (t0) and during each of the following two visits within the study (t1 6 months, t2 12 months).

Data from screened patients were reviewed to determine the subject eligibility. Subjects who met all inclusion criteria and none of the exclusion criteria were enrolled in the study and randomized to treatment.

The following treatment regimens were applied:

Statistical Analysis Plan Version no. 1.0 – 20/07/2020 Protocol Code NORFLO-ORO-16 EudraCT number NA

- NORFLO® ORO 1.7450 gr
- Placebo 1.7450 gr

### 4.3 Randomization and Blinding

Up to 60 eligible patients were randomly assigned to NORFLO® ORO or placebo treatment groups in a 1:1 ratio rusing a stratified randomization-blocks-scheme. The patient randomization list was generated-by-Latis S.r.l., using the procedure PROC PLAN of SAS 9.4 for Windows (SAS Institute Inc., Cary, NC, USA).

Due to the objectives of the study, the investigators, research staff, or patients did not know the treatment identity (test or control). The following study procedures were in place to ensure double-blind administration of study treatments:

Access to the randomization code was strictly controlled.

Packaging and labeling of test and control treatments were identical to maintain the blind.

The study blind will be broken on completion of the clinical study and after the study database has been locked.

### 5. STUDY ENDPOINTS

### 5.1 Primary Endpoints

The primary efficacy endpoint is the mean number and intensity of relapses per patient occurred during the study, from baseline to end of treatment, in patients treated with the NORFLO® ORO compared to patients treated with placebo.

The reduction in relapses was determined by a reduction of the intraocular inflammation through a clinical and diagnostic evaluation that includes Laser measurement of AC flare with Kowa LFM 600 or LFM 700 (Normal range 2.5-7 ph/ms, Outside normal range > 10 ph/ms).

The reduction of the mean number of relapses per patient between the year before treatment and the study period within each treatment group will also be assessed.

The reduction of cell damage and inflammation were measured by the Laser Flare Meter, in patients affected by HLA-B27-associated uveitis after treatment with NORFLO® ORO, when compared to placebo.

The number and intensity of relapses and LFM data, used in primary efficacy endpoints, were reported in the first unscheduled visit.

Only patients with relapses will be analyzed in primary efficacy endpoints.

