LFM measurements may be unreliable in eyes with extensive posterior synechiae or mature cataract due to increased background scattering of light. Seven measurements are usually obtained, the highest and lowest values are discarded and the mean and standard deviation of the remaining five readings are automatically calculated. Patients do not experience any pain or discomfort during measurements. Aqueous flare intensity has been found in the range of 2.9–3.9 ph/ms in healthy individuals between 20 and 40 years of age. Flare values have been found to increase slightly with age, reaching 5.0–6.5 ph/ms in subjects between 70 and 80 years of age. Flare values < 10 ph/ms are considered normal.

Effective management of uveitis requires a reproducible and quantitative method to determine and monitor intraocular inflammation. It has become evident that clinically meaningful changes in flare counts could be achieved both in low and high-flare situations because LFM allows measuring flares ranging between 3 and 1000 ph/ms on a linear scale. Gonzales *et al.* reported an inverse relationship between LFM flare and visual acuity in patients with uveitis. While no relationship was found between complications and anterior chamber cell or flare scores at the slit-lamp, a strong relationship was found between LFM flare and visual between LFM flare and complications such as posterior synechia and macular edema, highlighting the importance of utilized LFM as diagnostic tool.

HLA-B27-Associated Acute Anterior Uveitis

The inflammatory pattern of acute HLA-B27-associated anterior uveitis has been evaluated using LFM. In a study on 44 patients presenting an acute episode of anterior uveitis, the mean initial flare was 160 ± 22 ph/ms (range: 11–787 ph/ms). All patients were given standard therapy consisting of hourly instillations of 1% prednisolone drops progressively tapered after 3 days according to the evolution of inflammation. A 50% and 90% flare reduction occurred after 2 and 8 days, respectively, under the standard therapeutic regimen used. In 15 out of the 44 patients enrolled, an additional periocular corticosteroid injection was needed because of insufficient flare decrease (less than 30% of initial flare) or because of flare reduction occurred between 10h and 24h. The end of an episode of anterior uveitis was defined as a flare level below 8 ph/ms. This study demonstrates that LFM allows meticulous adjustment of therapy in patients with HLA-B27-associated uveitis.

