5 CRITERIA FOR EVALUATION

5.1 **Primary Efficacy Endpoint**

The primary efficacy endpoint will be the mean number and intensity of relapses per patient occurred during the study, from baseline to end of treatment, in patients treated with the NORFLO[®] ORO compared to patients treated with placebo.

The reduction in relapses will be determined by a reduction of the intraocular inflammation through a clinical and diagnostic evaluation that includes Laser measurement of AC flare

with Kowa LFM 600 or LFM 700 (Normal range 2.5-7 ph/ms. Outside normal range > 10 ph/ms).

The reduction of the mean number of relapses per patient between the year before treatment and the study period within each treatment group will also be assessed.

The reduction of cell damage and inflammation will be measured by the Laser Flare Meter, in patients affected by HLA-B27-associated uveitis after treatment with NORFLO[®] ORO, when compared to placebo.

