Effective management of uveitis requires a reproducible and quantitative method to determine and monitor intraocular inflammation. Clinically meaningful changes in flare counts can be detected both in low and high-flare values because LFM allows measuring flare values that range between 3 and 1000 ph/ms on a linear scale. Gonzales *et al.* reported an inverse relationship between LFM flare and visual acuity in patients with uveitis. While no relationship was found between complications and anterior chamber cell or flare scores at the slit-lamp, a strong relationship was found between LFM flare and complications such as posterior synechia and macular edema.Intra-ocular inflammation evaluation by the Kowa Laser Flare Meter examination will be done at baseline and at each following visit.

9.2.3 **OCT**

Optical coherence tomography (OCT) Spectralis[®] (Heidelberg Egineering, Heidelberg Germany) is a non-invasive imaging test that uses light waves to take cross-section pictures of your retina, the light-sensitive tissue lining the back of the eye.

Cross-sectional visualization is an extremely powerful tool in the identification and assessment of retina abnormalities. The high resolving power ($10\mu m$ - Time Domain, $5\mu m$ – Spectral Domain) provides excellent detail for evaluating the vitreo-retinal interface, neurosensory retinal morphology, and the RPE-choroid complex. The ability to perform volumetric and retinal thickness analysis also provides a quantitative and repeatable method to evaluate surgical and pharmacological interventions. Individual high resolution line scans are a simple way to identify overt as well as very subtle retinal interface pathologies, such as a persistently adherent posterior hyaloid, fine epiretinal membranes, and vitreomacular

traction. In a procedure that is easily tolerated by most patients, well-placed line scans can differentiate between pseudo holes, lamellar holes and full thickness macular holes with a high degree of confidence. Line scans can also confirm the presence of retinal edema from various causes. When combined with serial thickness map or volume analysis, these different data sets provide a detailed picture of disease progression or therapeutic response.

OCT Spectralis[®] examination will be done at baseline and at each following visit.

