## 11.4 Efficacy Analysis

## 11.4.1 Primary Efficacy Endpoints

The number and intensity of relapses were assessed through instrumental analysis and physical examination. These endpoints will be assessed from baseline to end of treatment.

When a relapse occurs, the data reported in the first unscheduled visit concerning the intensity of the relapse and data from LFM will be used as they are taken before the administration of both systemic and topical cortisone.

Mean and standard deviation will be used to describe the number of relapses per patient. The mean number of relapses per patient will be compared between the treatment groups using Student's t-test. ANOVA will be used to include predictive/confounding variables in the model.

In addition, a generalized linear mixed model (GLMM) with Poisson statistical distribution and with the number of relapses as dependent variable will be used to assess the effects of the treatment on reducing the number of relapses, also including in the model other potentially predicting/confounding variables.

The intensity of each relapse will be scored as mild (either trace to 1+ cell OR flare  $\leq 20$ ), moderate (2+ to 3+ cell OR Flare  $\geq 20$  and  $\leq 100$ ) and severe (4+ cell OR Hypopyon OR flare  $\geq 100$ ). For each patient, the average intensity will be estimated as the mean of the intensity of relapses observed during the study. The average and the maximum intensity will be compared between treatment groups using Student's t-test. ANOVA will be used to include predictive/confounding variables in the model. As this variable could likely be not normally distributed, Wilcoxon Mann-Whitney will be also used.

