## 11.5 Summary of Efficacy Analyses

| Endpoint   | Analysis  | Populations |
|--|---|-------------|
| The mean number and intensity of relapses
(primary endpoint)                | Student's t-test, ANOVA, generalized linear mixed model | ITT         |
| The reduction of mean number of relapses (primary endpoint)                    | Student's t-test, ANOVA                                 | ITT         |
| The difference of the level of cell damage and inflammation (primary endpoint) | ANCOVA  | ITT         |
| The changes in IOP (secondary endpoint)  | ANCOVA  | ITT         |
| The changes in OCT (secondary endpoint)  | ANCOVA  | ITT         |
| The changes in BCVA (secondary endpoint)                                       | ANCOVA  | ITT         |
| The presence of keratopathy (secondary endpoint)                               | Chi-square test   | JTT         |
| The presence of synechiae (secondary endpoint)                                 | Chi-square test   | ITT         |
| Information collected through the Quick questionnaire (secondary endpoint)     | Chi-square test   | ITT         |

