# 13. DEVIATIONS FROM THE PROTOCOL SPECIFIED ANALYSIS

The analysis of the number of relapses per eye will not be performed.

Nonparametric test will be used when the variables are not normally distributed.

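### The SAP takes the laser flare endpoint from the relapse visit in relapsing patients only, so it measures attack severity, and the 6- and 12-month readings have no stated analysis

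*SAP*

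**What the plan says.** **Protocol.** Section 5.1 places LFM under the primary endpoint: "The reduction of cell damage and inflammation will be measured by the Laser Flare Meter". Section 9.2.2 gives the timing: "Intra-ocular inflammation evaluation by the Kowa Laser Flare Meter examination will be done at baseline and at each following visit". Sections 10.1 to 10.3 and Appendix 1 confirm LFM for every patient at baseline, 6 months and 12 months. Section 14.3 compares the arms by ANCOVA with baseline flare in the model. It names no analysis visit and does not restrict the comparison to relapsers.

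**SAP.** Section 5.1 states: "The number and intensity of relapses and LFM data, used in primary efficacy endpoints, were reported in the first unscheduled visit". It then adds: "Only patients with relapses will be analyzed in primary efficacy endpoints". Section 11.4.1 says that when a relapse occurs "the data reported in the first unscheduled visit concerning the intensity of the relapse and data from LFM will be used", because these data precede cortisone treatment. The same section repeats the protocol's LFM ANCOVA without naming a visit. In section 11.5 the row "The difference of the level of cell damage and inflammation (primary endpoint") is assigned to the ITT population.

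Section 5.2 lists the endpoints taken from Visits 1, 2 and 3, and LFM is not among them. The only LFM table is 14.2.1.4, under the primary endpoints. Section 13 lists two departures from the protocol: the per-eye relapse analysis is dropped, and "Nonparametric test will be used when the variables are not normally distributed". The source of the LFM data is not mentioned there.

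**The concern.** The stated question is whether 12 months of product reduces intraocular inflammation. A reading taken at the start of an attack answers a different one: how high flare rises once an attack has begun.

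Three consequences follow.

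- **Baseline.** Inclusion criterion 2 requires a patient outside the acute phase, so the covariate is a quiet-eye value and the outcome is an acute one. A rise is built in, and no reduction can be estimated.
- **Selection.** A relapse-free patient has no relapse visit, and SAP section 9.1.4 replaces no missing data. Whether a patient contributes depends on relapsing, which the product is meant to prevent. The arms compared are then no longer the randomised arms. Deleting the relapsers-only sentence would not cure this.
- **Overlap.** The mild, moderate and severe score in SAP section 11.4.1 uses flare cut-offs of 20 and 100 from the same visit. Two results labelled primary would rest largely on one reading.

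**Working it through.** **1. The plan's own figure.** No sample size is given for LFM. The relapse-count figure reproduces. With difference 0.6, SD 0.7, two-sided 5% and 80% power, the normal approximation is n = 2 × (1.96 + 0.84)² × (0.7/0.6)² = 21.4, so 22 per arm. The t-test gives 22.4, so 23 per arm and 46 in total, as stated. With 20% dropout, 46/0.8 = 57.5, so 58 against the 60 recruited. The point below does not affect this.

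**2. The passages side by side.**

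| Source | LFM visit | Patients |
|---|---|---|
| Protocol 9.2.2, 10.1–10.3, Appendix 1 | baseline, 6 and 12 months | all |
| Protocol 14.3 | not named; ANCOVA on baseline | no restriction |
| SAP 5.1 | first unscheduled visit | relapsers only |
| SAP 11.4.1, relapse paragraph | first unscheduled visit | applies when a relapse occurs |
| SAP 11.4.1, ANCOVA paragraph | not named | not stated |
| SAP 11.5 | not named | ITT |
| SAP 5.2 and 14.2.2 | Visits 1–3 | LFM not listed |

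Of the scheduled readings, only baseline has a stated use, as covariate.

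**3. Readings without a stated analysis.** 60 patients × 2 visits = 120. With 20% dropout, 60 × 0.8 × 2 = 96. These are patient-visits; both eyes are examined each time.

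**4. Patients without an attack reading.** The means come from Protocol section 14.7. Poisson counts are my assumption, so the share with no relapse is exp(−mean):

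- placebo, 2.6: exp(−2.6) = 0.074, about 7%, leaving about 28 of 30;
- NORFLO ORO, 2.0: exp(−2.0) = 0.135, about 14%, leaving about 26 of 30;
- at 0.34, the post-treatment mean of the previous study: exp(−0.34) = 0.712, about 71%, leaving about 9 of 30.

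Poisson does not match the plan's SD of 0.7: it implies √2.6 = 1.61 and √2.0 = 1.41. A normal approximation with SD 0.7, counting values below 0.5 as no relapse, gives z = (0.5 − 2.6)/0.7 = −3.0 and (0.5 − 2.0)/0.7 = −2.1, so about 0.1% and 2%.

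**5. Precision.** Relative to 30 against 30 with equal variances, the standard error at the planned means is √[(1/28 + 1/26)/(2/30)] = 1.05 times as large.

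**6. Overlap with the intensity score (illustration).** Protocol section 2 cites 44 patients with mean attack flare 160 ± 22 and range 11–787 ph/ms. That range forces an SD of at least about 99, so 22 cannot be an SD. Read as a standard error it gives 22 × √44 = 146. With lognormal flare at SDs of 98 and 146, the simulated rank correlation of flare with a flare-only score is 0.79 to 0.86. It is 0.60 to 0.78 when an assumed independent cell grade is added and the worse of the two counts.

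**The case against.** A reader might infer more than the documents support.

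- **That the SAP overrides a visit fixed in the protocol.** The protocol names no LFM analysis visit. Its section 5.1 links flare to the assessment of relapses, and section 10.4 requires a complete ophthalmic evaluation at relapse visits. Use of Visits 2 and 3 is an inference from the schedule and the unrestricted, baseline-adjusted ANCOVA. I think it is the better reading, but it is not written down.
- **That the 6- and 12-month readings will certainly never be analysed.** SAP section 11.5 says ITT, section 11.4.1 is conditional on a relapse, and section 6.2 says the analysis follows both documents. Relapse-free patients might therefore keep scheduled readings. The relapsers-only sentence contradicts that. If it did apply, attack values in some patients would be mixed with quiet values in others.
- **That LFM merely repeats the intensity score.** Cells or hypopyon can also set the score, and intensity is averaged over relapses. Large overlap is what stands.
- **That precision collapses.** Pairing 0.34 with 2.6 gives √[(1/9 + 1/28)/(2/30)] = 1.48. Those are post- and pre-treatment means from an uncontrolled study of mixed aetiologies, and their difference of 2.26 is nearly four times the planned 0.6. Attack flare and quiet flare also need not share a variance.

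The pre-cortisone argument is sound for grading a relapse, but it does not make an attack reading a measure of reduction. Nor does a floor effect defend the choice: Protocol section 2 holds that "clinically meaningful changes in flare counts could be achieved both in low and high-flare situations".

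LFM's rank is also unclear. It is primary in Protocol section 5.1 and SAP section 11.5, a secondary objective in section 3.2 of both documents, and outside the testing hierarchy.

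**Conclusion.** The point holds as a conflict within the SAP and a mismatch between question and analysis. Followed literally, sections 5.1 and 11.4.1 give a comparison of attack severity among relapsers, under a label that promises reduction of inflammation.

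The change of question and the selection on relapse follow from the text alone. The numerical loss depends on relapse rates: slight at the planned means, even with Poisson counts, and considerable only if relapses are much rarer than planned. The overlap figures rest on assumed flare and cell distributions.

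The plan should be changed, but the relapse-count analysis and its sample size are untouched. LFM lies outside both the power calculation and the hierarchy.

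**What to change.** - Reconcile SAP sections 5.1, 11.4.1 (both paragraphs) and 11.5, and align Table 14.2.1.4 with them.
- Define the LFM endpoint as flare at the scheduled visits in all ITT patients with a reading. Make month 12 the main contrast, with month 6 as support or within one repeated-measures model.
- Use ANCOVA on baseline flare, with the eye rule stated in advance, since both eyes are measured and the SAP names neither.
- Where Visit 3 is missing, use the early-withdrawal reading (Protocol section 10.5) in a sensitivity analysis.
- Keep attack-visit flare, before cortisone, as a description of relapse severity.
- List any departure from the protocol in SAP section 13.

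The cost is SAP wording and one model on readings already scheduled, and it should be settled before unblinding. There is a small downside. Protocol section 10.4 lets Visits 2 and 3 move to about two months after topical treatment, and some withdrawn patients will have no later reading. The endpoint would therefore describe inflammation between attacks, and the SAP should say so.

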14.1 Data Sets Analyzed

All eligible patients who are randomized into the study and receive at least one dose of the study product (the Safety Population) will be included in the safety analysis. All eligible patients who are randomized into the study, receive at least one dose of the study product and have at least a post-randomization endpoint estimate (the Intention-to-Treat Population) will be included in the efficacy analysis.

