## 8. ANALYSIS POPULATIONS

# 8.1 Intent-to-Treat Population (ITT)

All eligible patients who are randomized into the study, receive at least one dose of the study product and have at \_\_\_\_ least a post-randomization endpoint estimate will be included in the efficacy analysis. Primary endpoints will be also analyzed in a modified Intention-to-Treat Population, where the patients with the protocol violations mentioned in the session 10.2 (Protocol Deviations) will be excluded.

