## 11.1 Analysis datasets

All eligible patients who were randomized into the study and received at least one dose of the study product (the Safety Population) will be included in the safety analysis. All eligible patients who were randomized into the study, received at least one dose of the study product and had at least a post-randomization endpoint estimate (the Intention-to-Treat Population) will be included in the efficacy analysis. Primary endpoints will be also analyzed in a modified Intention-to-Treat Population, where the patients with the protocol violations mentioned in the session 10.2 (Protocol Deviations) will be excluded.

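### SAP 5.1 limits the primary endpoints to patients who relapse, contradicting the assigned ITT population and dropping observed counts of zero

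*SAP*

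**What the plan says.** SAP 5.1 defines the first primary endpoint as the number and intensity of relapses per patient from baseline to end of treatment. It adds the change from the previous year and flare by Laser Flare Meter (LFM), and ends with two sentences:

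- The first gives the source of the data: "The number and intensity of relapses and LFM data, used in primary efficacy endpoints, were reported in the first unscheduled visit".
- The second sets the population: "Only patients with relapses will be analyzed in primary efficacy endpoints".

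The rest of the plan describes a different population:

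- SAP 8.1 starts from "All eligible patients who are randomized into the study, receive at least one dose of the study product" and asks only for a post-randomisation endpoint value. SAP 11.1 repeats it: patients who "had at least a post-randomization endpoint estimate (the Intention-to-Treat Population) will be included in the efficacy analysis". Protocol 14.1 has the same rule: "have at least a post-randomization endpoint estimate (the Intention-to-Treat Population) will be included in the efficacy analysis".
- The table in SAP 11.5 gives ITT as the population for all three rows marked primary.
- SAP 11.4.1 compares relapse counts by t-test and by a "generalized linear mixed model (GLMM) with Poisson statistical distribution and with the number of relapses as dependent variable", with no restriction to relapsers. Protocol 14.3 has none either.
- SAP 11.4.1 uses the first unscheduled visit for data "concerning the intensity of the relapse and data from LFM will be used as they are taken before the administration" (cortisone is meant), that is, for intensity and LFM and not for the count.
- SAP 13 lists the departures from the protocol analysis. This restriction is not among them.

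**The concern.** A patient followed without a relapse has a known count of zero. That is an endpoint value and the best result the trial can record. Leaving such patients out selects on a post-randomisation outcome that treatment is meant to change, so the groups compared are no longer the randomised groups.

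Three analyses in SAP 11.4.1 are affected on the literal reading:

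- **Relapse count.** The better the product prevents relapse, the more of its successes are removed.
- **Change from the previous year.** Entry requires at least one relapse in the prior year (protocol 6.2). If analysis also requires at least one on study, a patient who entered with exactly one can never show a reduction.
- **Responders.** Patients who go from a high count to zero disappear from the comparison.

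If the conflict stays open, the choice between the two readings could be made after the blind is broken.

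**Working it through.** **1. The plan's own figure.** Inputs from protocol 14.7 and SAP 7: 2.6 vs 2.0 relapses, SD 0.7, alpha 5%, power 80%, 20% dropout, 60 recruited. A two-sided two-sample t-test with effect size 0.6/0.7 = 0.857 needs 22.4, so 23 per arm, or 46 in total. This reproduces the stated number. Power is 82.8% at 24 per arm (60 × 0.8 = 48) and 90.4% at 30 per arm. The calculation makes no allowance for excluding relapse-free patients.

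**2. Dilution, no distribution assumed.** The mean among relapsers is the overall mean divided by the share who relapse. Hence

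ratio seen = true ratio × (share relapsing on placebo / share relapsing on product).

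If the product raises the relapse-free share, the ratio moves towards 1. Example with Poisson counts assumed at 2.6 and 2.0: relapse-free shares are exp(−2.6) = 7.4% and exp(−2.0) = 13.5%. The ratio goes from 0.769 to 0.769 × 0.926/0.865 = 0.82. The relapser means are 2.6/0.926 = 2.81 and 2.0/0.865 = 2.31, so the difference falls from 0.60 to 0.50.

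**3. Power, all patients → relapsers only.** 40,000 simulated trials per case, two-sided 5%. The Poisson model is a Wald test of the log rate ratio without a random effect, since the SAP specifies none.

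| Case (placebo vs product) | Relapse-free, placebo / product | t-test, 30/arm | t-test, 24/arm | Poisson model, 30/arm | Poisson model, 24/arm |
|---|---|---|---|---|---|
| 2.6 vs 2.0, SD 0.7, rounded to whole counts | 0.1% / 1.6% | 85.3% → 83.3% | 76.5% → 74.4% | – | – |
| 2.6 vs 2.0, Poisson assumed | 7.4% / 13.5% | 33% → 25% | 27% → 21% | 33% → 16% | 27% → 13% |
| 2.6 vs 0.34, Poisson assumed | 7.4% / 71% | 100% → 94% | 100% → 85% | 100% → 87% | 100% → 73% |
| 1.5 vs 0.75, rates and Poisson assumed | 22% / 47% | 78% → 37% | 68% → 29% | 79% → 10% | 69% → 6% |

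In the first row, rounding raises the SD to about 0.757, which is why the starting power is below the 90.4% and 82.8% of step 1. In the second row, the low starting power comes from Poisson variance, not from this rule. The third row uses the earlier study's before and after means (protocol 14.7).

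With equal Poisson rates between 0.75 and 2.6, the t-test among relapsers rejects in 4.6–5.1% of trials. The Poisson model rejects in about 2.6% at rate 2.6. False positives do not increase.

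**4. Change from the previous year, product arm.** Assumed: Poisson counts, one common rate for all patients in each period, prior count at least 1.

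| Rate before → on study | Enter with exactly one relapse | Mean fall, all → relapsers | Same, net of regression to the mean | Responders discarded |
|---|---|---|---|---|
| 2.6 → 2.0 | 21% | 0.81 → 0.50 | 0.60 → 0.50 | 16–20% |
| 2.6 → 0.34 | 21% | 2.47 → 1.63 | 2.26 → 1.63 | 71–72% |
| 1.5 → 0.75 | 43% | 1.18 → 0.51 | 0.75 → 0.51 | 49–57% |

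Regression to the mean is the prior mean given at least one relapse, minus the rate: 2.81 − 2.60 = 0.21 and 1.93 − 1.50 = 0.43. Responders discarded is P(0)/P(low category). The range reflects whether a count equal to the median is classed as high or low.

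**5. How common zeros might be.** The earlier study had 36 relapses in 106 treated patients, so at most 36 relapsed and at least 70 (66%) did not. It was uncontrolled and of mixed aetiology, so this is no forecast for the trial.

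**6. Keeping zeros requires follow-up time.** With 20% dropout and exit times assumed uniform over the year, early leavers supply 55% of all zeros at rate 2.6 and 44% at rate 2.0. Now assume no effect, rate 2.6, 30 per arm, and dropout of 10% on placebo and 30% on product. Raw means are 2.47 and 2.21. False positives are about 9% (t-test) and about 12% (Poisson without offset), against about 5% with a log follow-up offset.

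**The case against.** The best defence is that 5.1 is loose wording. The sentence follows one about first-unscheduled-visit data, and SAP 11.4.1 ties that visit only to intensity and LFM. The methods then analyse counts without restriction, and all three primary rows in 11.5 read ITT. This reading is plausible, but the preceding sentence in 5.1 also names the number of relapses and the restriction covers the primary endpoints without exception. Both readings have support, and that is itself the defect.

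On size, the loss is about 2 points on the plan's own mean and SD. The largest losses use rates found in neither document, and 2.6 vs 0.34 is an uncontrolled before-and-after contrast. This stands: those rows are illustrations. The rule also tends to weaken the trial and not to manufacture success.

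The responder comparison is not named in 5.1, in the hierarchy or in 11.5, so its coverage is an inference. It is, however, described under the primary efficacy heading of 11.4.1.

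The dropout split in step 6 is invented, and follow-up time would matter even without the disputed sentence. Patients withdrawn for systemic treatment of a relapse (protocol 10.4) are not zeros. The offset is still needed once zeros are retained, and it costs almost nothing.

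**Conclusion.** The concern holds. As written, SAP 5.1 contradicts the ITT assignment in SAP 8.1, 11.1 and 11.5 and in protocol 14.1. It adds an undeclared restriction and discards observed outcomes of zero. The textual conflict is certain; which reading the authors intended is not.

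The numerical harm depends on the relapse-free share, which the documents do not give for this trial. It is small on the planning figures and severe if many patients stay relapse-free, most of all for the Poisson model, which expects the zeros that have been removed. Because the issue is who enters the first-ranked primary analysis, it must be settled before unblinding whatever the size.

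**What to change.** Before the blind is broken:

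- Delete the sentence in SAP 5.1, or limit it to average and maximum relapse intensity, which are undefined without a relapse. Label that comparison non-randomised and supportive. Intensity is part of the first-ranked endpoint, so declare the change in SAP 13 and in the hierarchy.
- State that relapse number, change from the previous year and responder status are analysed in all ITT patients. A patient observed without relapse contributes 0 for the time observed, and this counts as a valid endpoint value.
- Add log follow-up time as an offset in the Poisson model. The t-test, the change and the responder comparison cannot carry one. Report follow-up by arm with them, and state in advance how patients observed for less than 12 months are handled.
- Confine the first-unscheduled-visit sentence in 5.1 to intensity and flare, in line with 11.4.1.
- For LFM, reconcile 5.1 and 11.4.1 with the ITT entry in 11.5 and label any relapser-only comparison non-randomised. The choice of visit remains the sponsor's.

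The cost is SAP wording and a little extra analysis, with no new data. The offset assumes that leaving is unrelated to later relapse risk. For patients withdrawn for systemic treatment, the relapse that led to withdrawal is counted but later ones are not seen.
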